5.6 Other Definitions

Baseline, Study Day and Event Duration are specifically defined as:

Baseline

Two baselines are defined:

- 1 Last assessment prior to first dose of study IMP on Day 0.
- 2 At 0 hours on Day 25 of the Confinement visit

Study Day

Study Day = (Date of event - first dose of study IMP) + 1.

Event Duration

Event Duration= (Date of resolution – Date of onset) + 1

6. Statistical Methods.

This statistical analysis plan specifies the requirements for the analysis and reporting of all data collected during the study.

All analyses and data reporting procedures will be undertaken using SAS® v9.4 in a Windows version 10 operating system environment.

The descriptive statistics produced will account for the nature and distribution of the data collected. For continuous variables (actual and percentage change from baseline), data will be presented as number (n), mean, median, standard deviation, and range. For discrete variables (Incidence, Response outcome) data will be presented as frequencies and proportions and the denominator will be the number of patients available.

Data collected from patients in each of the three cohorts (Part 1 AD, Part 1 PD, Part 2 PD) will be derived and summarised as described in section 5 and analysed according to the defined analysis population in section 4.

All comparisons of primary interest performed in Part 1 and Part 2 involve changes from baseline (Within treatment group). The null hypothesis throughout is that there is no difference between the Day 25 end of treatment and Pre-treatment baseline (H0. $X_{end}=X_{base}$, H1. $X_{end} \neq X_{base}$).

Between treatment groups comparisons are also possible (but of secondary interest due to the small sample size). Here the null hypothesis is that there is no difference between any of the treatment groups at the end of treatment (H0. Placebo= $X_{5mg}=X_{10mg}=X_{20mg}=X_{40mg}=X_{80mg}$, H1. Placebo $\neq X_{5mg} \neq X_{10mg} \neq X_{20mg} \neq X_{40mg} \neq X_{80mg}$).

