6.1 Pharmacodynamic Endpoints

For the Part 1 AD and Part 1 PD cohorts, each variable measured in plasma and CSF will be analysed using an analysis of variance (ANOVA) model of the percentage changes from Baseline (between Baseline Day 0 Pre-dose 0h and Day 25 Pre-dose 0h). This will include Treatment group as a fixed effect and LSmeans (with 95% CI) for this effect will be presented (Within group).

Between group differences for 80mg vs Placebo will be assessed and presented (LSmeans +/- 95% CI) although results will be viewed cautiously given small control group samples size.

Then the percentage change from Baseline (Day 25 Pre-dose 0h) for each of the 6 hourly assessments will be analysed using a Repeated measured mixed model (RMMM) including Treatment group as a fixed effect, Time as the repeated effect and Subject as random term. Compound symmetry will be assumed for the covariance/correlation matrix. An overall average LSmean (with 95% CI) for the Treatment effect will be presented together with individual LSmean (with 95% CI) estimates for each hour. Treatment group differences will also be presented for the comparison between 80mg vs Placebo but the same caveat used given the control group subject sample size.

The maximum percentage change from Baseline (Day 25 Pre-dose 0h) over the 6 hours will also be analysed with an ANOVA model for both the Within treatment group and Between group (80mg vs Placebo) comparisons.

In the event of either model failing assumptions of normality or constant variance, a log transformed analysis of the actual values (*not percentage change*) will be substituted and the output estimates (means and 95% CIs) then back transformed by exponentiation to enable presentation of the ratio of values (%).

For the Part 2 PD cohort with 4 treatment dose groups (5, 10, 20, 40mg) the same analyses models will be employed. However, the data from the Part 1 PD patients will also be included (for those biomarker variables retained from Part 1 after evaluation at that stage) from both the Placebo and 80mg patient groups and combined with the Part 2 data. Within and Between group ANOVAs and RMMM model analyses will then be employed in a similar manner to Part 1. The Part 2 report of treatment group differences will include Placebo (from Part 1) versus each of the five active treatment groups, namely 5mg, 10mg, 20mg and 40mg from Part 2, and 80mg group from Part 1.

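### SAP 6.1's fallback on log actual values carries no baseline term, so as written its within-group estimate is a concentration and not the ratio the plan says it will present

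*SAP*

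**What the plan says.** SAP 6.1 sets out three biomarker analyses, each on a change scale:

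- An ANOVA of the percentage change from Day 0 pre-dose to Day 25 pre-dose. On model terms it says: "This will include Treatment group as a fixed effect". The LS means for that effect, with 95% intervals, are the within-group results.
- A repeated measures mixed model (RMMM) of the percentage change from Day 25 0h at each of the six hourly assessments, with treatment fixed, time repeated and subject random.
- An ANOVA of the maximum percentage change from Day 25 0h over the six hours.

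The fallback follows: "In the event of either model failing assumptions of normality or constant variance", the plan turns to "a log transformed analysis of the actual values", with a parenthesis ruling out percentage change. This analysis "will be substituted and the output estimates (means and 95% CIs) then back transformed by exponentiation to enable presentation of the ratio of values", expressed in percent.

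SAP 2 and SAP 6 make the within-group change from baseline the comparison of primary interest. The null is that "there is no difference between the Day 25 end of treatment and Pre-treatment baseline". Between-group comparisons are secondary, and their null is stated for the end of treatment.

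**The concern.** In the main ANOVA, each patient's baseline is used in one place only, the denominator of the response. The fallback removes that response and puts nothing in its place: no baseline covariate, no visit term and no log ratio. SAP 7.2.1.1 to 7.2.2.2, which describe the output tables, do not mention the fallback. The specified model and the specified output therefore disagree.

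At stake is the model-based within-group result for every biomarker that triggers the fallback. The trigger is not remote. In the prior-study table in protocol 6.2, the standard error of the sAPPβ percentage change is 0.9151 at 1.5h (N=4) and 0.0519 at 6h (N=3). These imply SDs of 0.9151 × √4 = 1.83 and 0.0519 × √3 = 0.09, about a 20-fold range. The groups are tiny and the comparison is not the one planned here, so this is only a hint that constant variance may fail.

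Cohorts are also unblinded and reported at separate locks (SAP 1 and SAP 7). If the response is left to be inferred, it could be settled after unblinding or differently between reports.

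**Working it through.** **Inputs.** From the SAP: responses and model terms (6.1), null hypotheses (2 and 6), 10 active to 4 placebo per Part 1 cohort (3.3), two-sided 0.05 (3.1). The documents do not give the between-patient SD of log values or the Day 0/Day 25 correlation (rho). A log SD of 0.4 is assumed below, and rho is varied. The plan attaches no figure to the fallback, so there is none to reproduce.

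**1. What each response estimates.** Let Y0 and Y25 be the pre-dose values on Day 0 and Day 25, with treatment as the only model term.

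- Response log(Y25): exp(LS mean) is the group's geometric mean Day 25 concentration. The exponentiated active-minus-placebo difference is the ratio of Day 25 geometric means.
- Response log(Y25) − log(Y0): exp(LS mean) is the group's geometric mean Day 25/baseline ratio. The exponentiated difference is a ratio of ratios.

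**2. Illustrative records.** Baselines 200, 400 and 800 units, each falling 30%, give 140, 280 and 560 at Day 25.

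- Literal fallback: (140 × 280 × 560)^(1/3) = 280 units.
- Log ratio: (0.7 × 0.7 × 0.7)^(1/3) = 0.70, or 70% of baseline.
- If actual values meant Day 0 and Day 25 stacked, with treatment still the only term, the result pools both days. The baseline geometric mean is (200 × 400 × 800)^(1/3) = 400, so the estimate is √(400 × 280) ≈ 335 units, again a concentration.

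**3. The primary null.** Simulation of 4,000 runs, 10 versus 4 patients, pooled-variance ANOVA, log SD 0.4.

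- True active ratio 0.70: a baseline geometric mean of 200 units gives an exponentiated LS mean of about 140. A baseline of 0.2 units gives 0.14. The answer follows the assay unit, whereas the log ratio gives 0.70 in both cases.
- No true change, baseline 200 units, rho 0.8: the literal analysis returns about 200, and a test of LS mean = 0 rejects in 100% of runs because it asks whether the concentration equals 1 unit. The log-ratio test rejects in about 5%.

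**4. The RMMM.** Its baseline, Day 25 0h, is neither one of the six hourly values nor a model term. Its hourly LS means on log actual values likewise back-transform to concentrations.

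**5. Between-group precision.** With equal variance s² at both visits, Var(log Y25 − log Y0) = 2s²(1 − rho). Relative to the variance of log Y25 alone, this is 2(1 − rho).

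| rho (assumed) | 2(1 − rho) | Power, Day 25 levels | Power, log ratio |
|---|---|---|---|
| 0.3 | 1.4 | not simulated | not simulated |
| 0.5 | 1.0 | about 28–29% | about 28% |
| 0.8 | 0.4 | about 28–29% | about 59% |
| 0.95 | 0.1 | about 28–29% | about 99% |

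Power is for a true 30% fall on active, none on placebo, and log SD 0.4. Both analyses recover an active/placebo ratio of about 0.70 on average when the groups share the same expected baseline.

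**The case against.** The strongest reply is that the SAP does not intend a concentration. It names a ratio in percent as the output, applies the no-change null throughout, and in 6.4.2 uses ratios in percent for exponentiated differences of logs. The exclusion of percentage change can be read as a warning not to take logs of a quantity that may be negative. A value in assay units would look wrong in a ratio column and might be caught in programming. The fallback sentence also does not list its own model terms, and the table shells in Appendix 1 are not in the text at hand. All this shows that a ratio was meant. It does not supply the response or term that would produce one, and a programmer who infers the log ratio has to depart from the words about actual values.

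A reader might go further and infer three things the documents do not support.

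- **That the between-group comparison becomes invalid.** It remains a ratio, and the SAP's between-group null concerns the end of treatment, which a ratio of Day 25 levels does address. The inconsistency is with 6.1 and 7.2, where the main analysis compares changes. These contrasts are secondary and are to be read cautiously.
- **That power must fall sharply.** This holds only at high correlation. The nearest figures in the documents, the 0h percentage-change standard errors in protocol 6.2 (0.2493 for sAPPα and 0.2227 for sAPPβ, N=4), imply SDs of about 0.50 and 0.45. They come from very few patients and a different scale, and they give no reason to assume a large gain from the log ratio.
- **That an assay shift between Parts 1 and 2 would bias the placebo contrasts.** No shift is documented. It would cancel in a within-patient ratio only if it were multiplicative and common to both of a patient's samples, and the documents do not say how samples are batched.

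**Conclusion.** The point holds for the within-group estimate. Followed as written, the fallback gives a concentration where the plan promises a ratio, and it does not test the null the SAP calls primary. This follows from the stated response and terms and needs no assumed variance. It does assume that the fallback inherits the terms of the models it replaces; SAP 6.1 states no others.

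For the between-group contrast the conclusion is narrower. The fallback compares Day 25 levels without baseline adjustment, while the main analysis compares changes. The effect on precision cannot be stated from the documents: none at a correlation of 0.5, a loss above it, a gain below it.

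The reach is limited. Only biomarkers that trigger the fallback are affected, and SAP 7.2 still summarises actual values, change and percentage change by treatment group. The biomarkers are exploratory in the protocol, whose primary outcomes are safety and plasma PK. It would be too strong to say that the within-group evidence disappears. What is lost is the model-based estimate and its interval.

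**What to change.** In SAP 6.1, replace the log analysis of actual values with an analysis of the within-patient log ratio, defined for each model:

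- Day 0 to Day 25 ANOVA: log(Day 25 0h) − log(Day 0 0h).
- RMMM: log(Day 25 hour h) − log(Day 25 0h), for h = 1 to 6.
- Maximum-change ANOVA: log of the selected extreme hourly value − log(Day 25 0h), with the extreme chosen by the same rule as in the main analysis.

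State that exponentiated LS means are within-group ratios (%), tested against 100%, and that exponentiated differences are ratios of ratios against placebo. Any precision claim made for the change should be shown over a range of assumed correlations.

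The cost is a few lines of SAP text and a small programming change, with no new data. The wording should be settled before a cohort's data are unblinded, so that all reports use the same response.

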Posiphen's safety has been established in three Phase I clinical studies by [name] et al. Importantly, Posiphen normalized levels of α SYN, APP, and tau in the cerebrospinal fluid (CSF) of mildly cognitively impaired (MCI) patients at a dose of 4x60 mg/day (Protocol QR12001). Preclinical data proves Posiphen's efficacy in restoring colonic motility in a human *SNCA*^{453T} tg mouse model of early PD, in restoring memory and learning in an *APP/PS1* transgenic (tg) mouse model of AD, restoring axonal transport in DS trisomic mice, preserving memory and learning in traumatic brain injury rats and preserving the retina in acute glaucoma.

α SYN, APP, and tau contribute to the progression of AD and PD in similar ways: they impair axonal transport and lower neurotransmitter and neurotrophic factor release, they cause inflammation, they form aggregates, and, finally, they lead to nerve cell death. In our *in vitro* and *in vivo* preclinical studies, Posiphen has normalized all those actions.

We have conducted a proof-of-concept study in mildly cognitive impaired patients at 4x60 mg/day (Protocol QR12001) and found that Posiphen lowers levels of neurotoxic proteins and of inflammatory markers. Presently, we are testing Posiphen in the DISCOVER study at 1x60, 2x60 and 3x60 mg/day for up to 25 days to see if it changes the synthesis and degradation

kinetics of A β in a stable isotope labelling kinetic (SILK) study. The DISCOVER study is ongoing through the ADCS and is planned for 24 patients to be enrolled; currently, approximately half of the study has been enrolled, and there have been no severe AEs or SAEs attributed to Posiphen reported.

From our animal data, we found that Posiphen works in more than Alzheimer animals, because it inhibits more than one neurotoxic protein. We found that in transgenic AD and PD animals it lowers levels of neurotoxic proteins and restores the affected function. Therefore, we want to test Posiphen in a comparison study of AD and PD patients and measure not just target engagement, but also pathway engagement.

From our animal data, we also found that the doses used to show an effect on neurotoxic proteins are very high and that we can see an effect of Posiphen at much lower doses. Therefore, we are testing Posiphen in a randomized dose de-escalation study to see what the lowest effective dose is in humans.

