6.1 Randomization

Subjects who have signed an informed consent and meet screening eligibility requirements will be randomly assigned to the active and placebo treatment groups (10 randomized to Posiphen and 4 to Placebo for AD and PD, respectively) in Part 1. In Part 2, 40 Early PD patients will be randomly assigned, 10 patients each to one of the 4 different dose levels of Posiphen (5, 10, 20 or 40mg).

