2.1.4 Pharmacokinetics

PK parameters of the parent drug, posiphen, will be determined for both AD and PD patients at 80mg QD dose group after 25 days of repeated dosing (Part 1) and for PD patients at 5, 10, 20, 40mg QD after 25 days of repeated dosing for PD patients (Part 2).

Specific parameters of interest are Area under the curve (AUC 0-t, 0-inf), maximum concentration (Cmax), time of maximum concentration (Tmax), half-life (t_{1/2}), and clearance (CL).

3. Study Design.

This study will be conducted in two parts: Part 1 will evaluate the safety, tolerability, and pharmacokinetics of Posiphen in 14 Early AD and 14 Early PD patients at 80 mg QD.

Each group will include 14 Early AD patients, randomly assigned, 10 to posiphen and 4 to placebo and 14 Early PD patients randomly assigned, 10 to Posiphen and 4 to placebo.

Part 1 will also include exploratory measures of pharmacodynamics and efficacy of Posiphen with target engagement, pathway engagement and functional/cognitive measures, including the degree of memory loss and cognitive function in AD patients as well as the degree of motor impairment and non-motor symptoms and quality of life in PD patients.

Part 2 will evaluate the safety, tolerability, and pharmacokinetics of posiphen in 40 patients with early PD, who will be randomly assigned to each of 4 dose levels; 5 mg QD, 10 mg QD, 20 mg QD and 40 mg QD.

Part 2 will also include exploratory measures of pharmacodynamics and efficacy of posiphen in Early PD patients with target engagement, pathway engagement and functional/cognitive measures, including the degree of motor impairment as well as other non-motor symptoms and quality of life in PD patients.

Full clinical details are given in the protocol.

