6.2 Functional Cognitive Endpoints

Prior to any formal statistical analyses of the cognitive and functional endpoints, each question, sub-domain and total score will be descriptively summarised and evaluated. Subsequently, formal statistical analysis of individual questions will only be performed and reported if any notable change from baseline is observed in the descriptive summaries. This process will be repeated at each analysis stage, i.e. Part 1 PD, Part 1 AD and Part 2 PD database locks.

For the Part 1 AD and Part 1 PD cohorts, the variables will be analysed using an ANOVA model of the Change from Baseline (Day 25 - Day 0). This will include Treatment group as a fixed effect, and LSmeans (with 95% CI) for this effect will be presented (Within group) together with Effect sizes ($(X_{Day\ 25} - X_{Base})/SD$). Between treatment group differences will also be presented for the comparison between Placebo and 80mg but interpreted cautiously.

For the Part 2 PD cohort with 4 treatment dose groups (5, 10, 20, 40mg) a similar ANOVA will be employed. However, the data from the Part 1 PD patients will also be included from both the Placebo and 80mg patient groups and combined with the Part 2 Parkinson patient data. Within and Between group ANOVA model analyses will then be employed in a similar manner to Part 1. However, in the Part 2 report, treatment group differences will include Placebo (from Part 1) versus each of the five active treatment groups, namely 5mg, 10mg, 20mg and 40mg from Part 2, and 80mg group from Part 1.

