Once all patients in Part 2 have completed, the PK data and infective particle and exosomes data from all three cohorts will be made available and analysed separately.

Summaries will be presented by cohort and treatment, visit and time recorded as appropriate.

The table below summarises the schedule for presentation of each cohort's statistical report output:

Analysis	Cohort	Deliverables
1	Part 1 – PD Patients (14)	Disposition Tables and Listings Biomarker* Tables, Figures and Listings Functional/cognitive Tables, Figures and Listings Safety Tables and Listings
2	Part 1 – AD Patients (14)	Disposition Tables and Listings Biomarker* Tables, Figures and Listings Functional/cognitive Tables, Figures and Listings Safety Tables and Listings
On completion of Part 2:		
3	PD Patients (54) – including 14 PD patients from Part 1 and 40 PD patients from Part 2	Disposition Tables and Listings Biomarker* Tables, Figures and Listings Functional/cognitive Tables, Figures and Listings Safety Tables and Listings
4	PD Patients (50) – including ten 80mg PD patients from Part 1 and forty PD patients (5mg, 10mg, 20mg and 40mg) from Part 2 AD Patients (10) – 80mg patients from Part 1 All patients (68) from Part1 and Part 2	PK analyses Tables, Figures and Listings PK analyses Tables, Figures and Listings Infective Particles in CSF: Tables, Figures and Listings Exosomes in plasma: Tables, Figures and Listings

*Biomarker results (excluding infective particles and exosomes) from assays conducted in Part 1 will be evaluated by the Sponsor and will inform the choice of assays and subsequent output from Part 2

NB: Infective particles and exosomes biomarker data will not be presented until after the completion of Part 2

Detailed ‘table shells’ for Part 1 and Part 2 will be produced to accompany this SAP. These not only describe table layout but table numbering formats and also the level of accuracy (number of decimal places) to be described in each table.

The following described tables and figures will be included in the statistical report.

7.1 Study Status.

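### For biomarkers and function, the only named Part 2 between-group contrasts set each randomised dose against four non-concurrent Part 1 placebo patients; the randomised dose comparison is planned for PK alone

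*SAP*

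**What the plan says.** Protocol section 2 gives the reason for the dose range: "we are testing Posiphen in a randomized dose de-escalation study to see what the lowest effective dose is in humans". Protocol 6.1 sets the allocation: "40 Early PD patients will be randomly assigned, 10 patients each to one of the 4 different dose levels of Posiphen". Part 2 has no placebo arm. The PD placebo patients all come from Part 1, described in SAP section 3: "14 Early PD patients randomly assigned, 10 to Posiphen and 4 to placebo".

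SAP sections 2 and 6 make each group's change from its own baseline the comparison of primary interest. They rank between-group comparisons second because the groups are small, under a null that all six groups (placebo and five doses) are equal.

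The between-group contrasts that are named for Part 2 are these:

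- Biomarkers, SAP 6.1: "The Part 2 report of treatment group differences will include Placebo (from Part 1) versus each of the five active treatment groups".
- Functional and cognitive scores, SAP 6.2: "in the Part 2 report, treatment group differences will include Placebo (from Part 1) versus each of the five active treatment groups".
- The output lists in SAP 7.2.1.1, 7.2.1.2 and 7.2.3 follow the same pattern.

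The model has treatment group as its only fixed effect (plus time and subject in the repeated-measures version). The caution in SAP 6.1 concerns the size of the control group. Non-concurrence is not mentioned.

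Only PK has comparisons among doses. SAP 6.4.2 plans all pairwise differences by the Scheffé method and a log-dose slope for Cmax and AUC.

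Part 1 data enter the Part 2 biomarker analysis "for those biomarker variables retained from Part 1 after evaluation at that stage". The note to the table in SAP section 7 says the Part 1 biomarker results "will be evaluated by the Sponsor and will inform the choice of assays and subsequent output from Part 2".

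**The concern.** Patients are randomised among four doses, but for biomarkers and function no named analysis compares those doses with each other. A within-group change does not use the randomisation and cannot separate a drug effect from anything else that changes over 25 days. The placebo contrasts for 5 to 40 mg do not use it either, because the placebo patients were randomised against 80 mg in Part 1.

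These contrasts also share their error. If the 4 placebo patients drift by chance, or if change from baseline differs between the parts, all four Part 2 doses shift in the same direction. That would look like an effect reaching down to 5 mg, which is the finding the study hopes for. Nor can the model adjust for it. No treatment occurs in both parts (placebo and 80 mg only in Part 1, 5 to 40 mg only in Part 2), so a Part effect cannot be separated from the dose-versus-placebo difference.

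**Working it through.** **Inputs.** 4 PD placebo patients (SAP section 3), 10 patients per dose (Protocol 6.1), two-sided 5% and 80% power (SAP Table 1), planning effect 1.4 SD (Protocol 6.2). Results are in units of the common SD of the change. Pooled residual df are 54 − 6 = 48.

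**The plan's own figure.** Protocol 6.2 gives N = 9 at 1.4 SD. Two-sample normal formula: 2 × (1.960 + 0.842)² / 1.4² = 8.01, rounded up to 9. This reproduces, but as a per-arm size for two equal arms. The named contrast is 10 versus 4. At 1.4 SD and 48 df its power is 64%, and 80% power needs 1.69 SD.

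**Precision.**

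- Dose versus Part 1 placebo: √(1/4 + 1/10) = 0.592. The 95% CI half-width is 2.011 × 0.592 = 1.19 SD.
- Dose versus dose within Part 2: √(1/10 + 1/10) = 0.447.
- Log-dose trend, 5 to 40 mg. With doublings coded −1.5, −0.5, 0.5, 1.5, the sum of squares is 5 per patient set and 10 × 5 = 50 in all. SE of the 5-to-40 mg difference is 3/√50 = 0.424.
- Correlation between two placebo contrasts: (1/4) / (1/4 + 1/10) = 0.714.

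The first SE belongs to a different question from the other two, so the figures show what each contrast can deliver, not that one replaces another.

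**False positives.** Simulation with no drug effect, normal data, 48 df, 400,000 replicates. Chance that at least one of the four Part 2 doses differs from placebo at two-sided 5%:

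| Assumed between-part difference in change from baseline | Any of four doses |
|---|---|
| none | about 12.5% |
| 0.25 SD | 16% |
| 0.5 SD | 27% |

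The shift sizes are assumptions; the documents give none.

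**Biomarker retention.** The documents state no retention rule, so two are compared. Bias means the average shift of every Part 2 placebo contrast in the favourable direction. The last column is the chance of at least one significant favourable dose, which is about 6% without selection.

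| Assumed retention rule (Part 1 PD) | Bias | Favourable significant dose |
|---|---|---|
| 80 mg minus placebo, better half | 0.34 SD | 12% |
| 80 mg minus placebo, best quarter | 0.54 SD | 22% |
| 80 mg within-group change, either cut | 0 | 6% |

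For the first rule the bias is 0.25/√0.35 = 0.423 times the mean of a standard normal above the cut: 0.423 × 0.798 = 0.34 for the better half and 0.423 × 1.271 = 0.54 for the best quarter. Under the second rule the placebo mean plays no part in selection, so nothing carries over.

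**The randomised alternative.** A log-dose trend on the 40 Part 2 patients (38 df) has 80% power for a 5-to-40 mg difference of 1.22 SD. Six unadjusted pairwise tests would give at least one false positive in about 20% of null cases, so they should not be added without adjustment.

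**The case against.** Pharmacodynamics and efficacy are exploratory, the lowest-effective-dose aim appears in the protocol's introduction and not in its objectives, and the SAP already ranks between-group comparisons second and asks for caution. This stands, and it limits the severity. The caution is about group size, though, and does not warn that the 5 to 40 mg contrasts are non-randomised.

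Some stronger readings are not supported:

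- *A reader might infer that the placebo contrasts are the main basis for inference, or that the randomisation is never used.* The primary comparisons are within-group. PK uses the randomised doses, and the six-group null includes them, although rejecting it identifies no dose. The 80 mg versus placebo contrast is randomised and concurrent within Part 1.
- *A reader might infer that any difference between the parts biases the result.* The endpoint is change from the patient's own baseline. A level difference, or a proportional assay shift affecting both samples alike, cancels in a percentage change. Only a difference in change matters. Protocol 6.7 and SAP 3.2 also describe identical conduct and uninterrupted recruitment.
- *A reader might infer that reusing the placebo patients necessarily biases the retained biomarkers.* That depends on the unstated rule and can be zero. The SAP also places evaluation after both Part 1 cohorts, so AD data may contribute.
- *A reader might infer that Part 2 patients all know they are on active drug.* This is plausible from the design, but the documents do not settle it; the Part 2 description in Protocol 4.2 still mentions placebo at the last dose.

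The best remaining objection is that a dose trend answers a different question. If the effect is flat over 5 to 40 mg, which the sponsor's expectation of activity at low doses makes plausible, the trend will be null. That stands and limits what the fix can deliver.

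**Conclusion.** The point holds in this form. For biomarkers and functional/cognitive scores, the SAP relies on within-group changes first and on non-randomised, non-concurrent contrasts with 4 placebo patients second, and it names no analysis of the randomised dose comparison. The SE of 0.59 SD and correlation of 0.71 follow from the planned group sizes and a common SD. The 12.5% figure adds normality and no multiplicity adjustment. The 16% to 27% range rests on assumed shifts. The retention bias runs from 0 to 0.54 SD over the assumed rules and should be reported as conditional. This is a change that should be made, not a flaw that invalidates an exploratory study.

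**What to change.** In SAP 6.1, 6.2 and 7.2:

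1. Add a Part 2-only model of the four randomised doses for each retained biomarker and each functional/cognitive score. Report one linear trend in log dose (estimate and 95% CI) and name it the randomised dose-response analysis. Make pairwise dose differences descriptive or multiplicity-adjusted, as already done for PK.
2. Keep the contrasts of 5 to 40 mg with Part 1 placebo, labelled in text and tables as non-randomised and non-concurrent.
3. State that the repeated 80 mg versus placebo result in the Part 2 report is not new evidence, because Part 1 data informed the choice of biomarkers.

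The cost is SAP wording and one extra model per endpoint; no new patients or samples are needed. The limitation should be written down too: the trend shows dose-dependence only. A flat effect over 5 to 40 mg would still rest on the within-group and placebo comparisons, and the trend alone cannot establish the lowest effective dose.
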